Dehydration is a complex condition resulting in a reduction in total body water (6), including water loss dehydration (due to water deficit, which can be hypernatraemic or hyponatraemic in the presence of hyperglycaemia) and salt loss dehydration (due to salt and water deficit, generally hyponatraemic, rarely isotonic). The reference standard for water loss dehydration is debated. While serum osmolality is a strong contender, disadvantages include slow response to dehydration and rehydration (14), but these are outweighed by its advantages. Advantages include that it can be measured at a single assessment (change in weight over a short period signals change in hydration but requires assessment over several days), is associated with health outcomes, and directly measures amounts of effective solute in plasma - as these solutes are impermeable to cell membranes they influence cell volume via their osmotic force on cells. Abnormally raised osmolarity implies dysregulation in multiple organ systems, and cell dehydration as intracellular fluid moves to extracellular space to reduce the osmolarity, shrinking the cells (15). Community dwelling elders with serum osmolality ≥300mOsmol/L had a 40% increased risk of 8 year mortality (RR 1.4, 95% CI 1.0 to 1.9, multivariate adjustment), and greater risk of new disability over 4 years (RR 2.1, 95%CI 1.2 to 3.6, multivariate adjustment) compared to those with normal osmolality (16). Salt loss and isotonic dehydration are also important, but differ from water-loss dehydration, requiring distinct treatment (with isotonic fluids). Hyponatraemia is less common and less predictive of outcome than increased osmolarity in older people (associated with 25% increase in 5-year mortality (2)), so needs to be studied separately (6).

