Effective osmolality is a function of sodium, potassium and glucose, and either serum sodium or glucose levels will be raised in water loss dehydration. Current dehydration (serum osmolality >300 mOsmol/kg), which develops following impending dehydration (295-300 mOsmol/kg), can be a medical emergency and 17% of those admitted to hospital with a main diagnosis of dehydration die within 30 days (2). If we can diagnose impending dehydration and prevent current dehydration this may improve life for older people and reduce health costs. Impending dehydration may cause poor health in its own right, so diagnosis of impending dehydration may improve health and quality of life for older people, but this will not be clear until we can diagnose and address impending dehydration. For these reasons this research will focus on water-loss dehydration, with serum osmolality as reference standard

Dehydration prevalence in frail older people varies by setting, level of care required, social deprivation and how hydration status is assessed. 4% of the growing number of older people in the UK live in a care home or long-stay hospital (rising to 21% of those aged 85+) – this is an extremely frail population (17). In Norfolk care homes we found that on a single assessment 30%

of 56 residents living in six care homes were dehydrated (with a furrowed tongue) (18), while a Californian nursing home study found 31% dehydrated at some point over 6 months (19).

Dehydration is more common as we age as our thirst response (20) and total body water (TBW) both reduce (10;21), and medications and increased dependence on carers increase dehydration risk (7). Contributors to low fluid intakes include clinical (dysphagia, functional impairment, dementia, and pain), social (lack of attention to drink preferences, inability of residents to communicate with staff, and lack of social support) and institutional factors (untrained and unsupervised staff). Water-loss dehydration, like falls or anaemia where identified, needs to be investigated to assess its causes, before addressing underlying problems. Where reduced fluid intake or increased losses are indicated, suggested interventions to prevent or reverse dehydration in older adults living in care homes include education and involvement of care staff, use of social times, drinks carts and water jugs, encouraging relatives to drink with residents, monitoring urine colour, and supporting those with swallowing problems (3;7).

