This will be a cohort study (researchers will be blind to reference standard results when assessing index tests). The design of this research incorporates understanding gained from the current literature on dehydration (summarised above), advice from members of PPIRes, discussions and debates with research mentors and steering group, results from (and debates during development the protocol for) our current systematic review of diagnostic accuracy of clinical and physical signs of water-loss dehydration in older people (which includes many current researchers in dehydration within the author group (25)), advice from the NIHR interview panel (who will be funding this research) and our ethics committee, discussions with care home managers and staff during the process of recruiting homes interested in participating in this research.

We will carry out primary research to improve identification of dehydration in residential care, assessing the diagnostic accuracy of clinical or physical signs that appeared promising in the diagnostic systematic review (25). Serum osmolality will be the reference standard for water-loss dehydration (295-300mOsmol/kg impending, >300mOsmol/kg current dehydration). As serum osmolality is not commonly available in residential care, a simple decision tree of tests to be carried out day to day by older people or their carers would be desirable.

Sample size: we will recruit 200 participants. Using the Kappa statistic as a measure of diagnostic accuracy and assuming a dehydration prevalence (current or pending categorised together) of approximately 40%, a sample size of 180 would ensure a standard error of no more than 0.05 for Kappa values in excess of 0.75. 200 participants recruited would allow for 10% to

terminate assessment before all signs are assessed or to provide unreadable blood samples. For values of at least 0.6, the standard error would be no more than 0.06. Thus, this sample size should provide an estimate of diagnostic accuracy with a precision to allow an assessment of the practical utility of the identified signs. Our previous experience of approaching 6 care homes with 213 residents recruited 50 participants to provide blood samples. Our potential set of participants for this study will be smaller as we will exclude those with diagnosed heart failure or renal failure, suggesting that approaching ~50 care homes will provide enough participants.

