At 1 year the care home manager will be asked to report on live status of all baseline participants. For those still alive and living in the care home we will ask for information to complete the Barthel index (from the care manager) and ask residents for permission to re-interview them. If this is acceptable we will re-assess quality of life and ask whether they feel that they drink enough to remain healthy. As the EuroQoL is very brief and non-invasive we will not formally re-assess capacity or formalise consent. For all participants (present and live or not) we will ask the manager whether they have experienced an episode of dehydration, the participants use of healthcare in the preceding year, and we will ask the manager more general questions about the positive and negative effects of the DRIE study on the care home over the past year. Those who remain within the care home will be approached, the study re-described and we will ask if the resident would be happy to participate in the follow up meeting. If so, this will take place immediately, participants, and their quality of life assessed.

2 year data collection:

At 2 years the researchers will contact the care manager to ask about live status of the resident and their functional status. The resident themselves will not be re-interviewed. Consent will be gained for this at baseline.

Data analysis: Data will be entered into an access database to be stored, cleaned and analysed. Assessment of water-loss dehydration will be on the basis of serum osmolality, a binary variable (i.e. hydrated or dehydrated, cut-off at 295mOsm/kg). Initial univariate analyses will be conducted to assess the diagnostic value of each considered factor. Those showing the best diagnostic accuracy will be considered collectively. 'Classification and Regression Trees' (CART (35)) will be used to develop a decision tree to diagnose impending and current water loss dehydration, while minimising the testing load required by residents and staff. The use of CART allows a greater flexibility over, say, logistic regression in which all predictor variables need to be assessed. Using a CART approach, it should be possible to use predictor variables in a more sequential fashion, thus avoiding the necessity of assessing every sign for every individual before a diagnostic can be made. Papers written will conform with STARD reporting standards for diagnostic studies (36).

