The cohort data gathered will be used to assess the consequentialist effects of dehydration (assessed by the developed diagnostic tool, and by measured serum osmolality) assessing the relationship between impending or current water-loss dehydration and mortality, change in functional status (Barthel Index) and QoL from baseline to 1 year in older care home residents. To maintain the power of the study we will ascertain mortality and functional status at 1 year (from care staff) of all participants who give informed consent and provide baseline data, even if they withdraw or are unable to provide informed consent for the final assessment. To assess potential confounding multivariate models will be adjusted for baseline age, gender, functional status, BMI, diabetes and other chronic illness, cognitive impairment, creatinine and number of medications. Cox proportional hazards models will be presented using hazard ratios (and 95% CIs). Secondary analyses will be carried out using the 2 year data, in the same way.

Position of this study in the 3-year funded research plan

This study is part (sections 2 and 3 below) of a 3-year NIHR funded research (as a Career Development Fellowship, also including considerable training) which aims to improve the health and wellbeing of older people living in the community through:

- 1. Systematic review (and summary) of research on prevention and reversal of impending waterloss dehydration, making best evidence accessible to UK health and social care workers,
- 2. Primary research to identify a simple decision tree of dehydration signs in residential care so that prevention and treatment strategies can be rapidly mobilised,
- 3. Clarifying associations between dehydration and health, functional status and quality of life in frail older adults,
- 4. Development and dissemination of an evidence-based statement of appropriate action to be taken when dehydration is identified in older people living in care homes to improve hydration in older people, and
- 5. A pilot study of the developed dehydration tool (decision tree of clinical signs) to assess its practicality, invasiveness, acceptability, and diagnostic accuracy in a different context,

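### As the only stated osmolality exposure, the 295 mOsm/kg split cannot tell the cohort models whether risk lies in impending dehydration or only above 300, and it probably costs precision

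*Protocol*

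**What the plan says.** The Data analysis part of the Methodology opens with a general definition: water-loss dehydration rests on "serum osmolality, a binary variable (i.e. hydrated or dehydrated, cut-off at 295mOsm/kg"). Univariate accuracy analyses and the classification tree follow.

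The next paragraph covers the cohort outcomes. Dehydration is to be classified both by the new tool and by osmolality as measured in blood, and the stated purpose is "assessing the relationship between impending or current water-loss dehydration and mortality", change in Barthel Index and quality of life. Mortality is to be reported as Cox hazard ratios, and the 2-year data are to be analysed in the same way. No continuous or three-level exposure is named.

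Elsewhere the Protocol distinguishes two levels. Study design gives "295-300mOsmol/kg impending, >300mOsmol/kg current dehydration". The Background says "Impending dehydration may cause poor health in its own right". The one prognostic estimate by osmolality level sits at the upper threshold: "Community dwelling elders with serum osmolality ≥300mOsmol/L had a 40% increased risk of 8 year mortality" (RR 1.4, 95% CI 1.0 to 1.9). Secondary aim 3 is to understand how baseline hydration status relates to mortality, quality of life and function at 1 and 2 years.

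**The concern.** A classification tree and sensitivity/specificity need a yes/no target, so a single cut is natural there. An outcome model does not need one. Carried into the cohort analysis, the cut merges 295-300 with everything above 300. It also treats all values below 295 as equal, and all values from 295 upwards as equal, although every participant has a number.

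Two things are at stake for secondary aim 3. The first is interpretation: one pooled hazard ratio does not show where on the scale the risk lies. That matters for the screening and intervention trials in impending dehydration that the Protocol says this work prepares for. The second is precision, in a cohort of about 200 frail residents whose size was set for diagnostic accuracy and not for outcomes.

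**Working it through.** **Inputs from the Protocol.** Prevalence: "assuming a dehydration prevalence (current or pending categorised together) of approximately 40" per cent. Evaluable residents: 180 of 200 recruited. Cuts: 295 and 300. Reference risk: RR 1.4 at or above 300. Not given, and therefore assumed below: the osmolality distribution, the share above 300, the shape of risk and the number of deaths.

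**The plan's own figure.** The Protocol says "a sample size of 180 would ensure a standard error of no more than 0.05 for Kappa values in excess of 0.75". With both margins at 0.40, chance agreement is 0.4² + 0.6² = 0.52. At kappa 0.75, observed agreement is 0.75 × 0.48 + 0.52 = 0.88, and SE = √(0.88 × 0.12 / 180) / 0.48 = 0.0505. At kappa 0.6, agreement is 0.808 and SE = √(0.808 × 0.192 / 180) / 0.48 = 0.0612. The Fleiss-Cohen-Everitt form gives 0.0504 and 0.0609. The statements hold after rounding, and 180 / 0.9 = 200. This calculation concerns diagnostic accuracy. The Protocol gives no precision or power for the cohort models.

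**1. What pooling hides.** Suppose residents at 295-300 carry no excess risk, those above 300 carry RR 1.4, and 40% are at or above 295. With a share p₂ above 300, the pooled RR is about [(0.40 − p₂) × 1.0 + p₂ × 1.4] / 0.40.

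| Share above 300 (assumed) | Pooled RR |
|---|---|
| 10% | 1.1 |
| 20% | 1.2 |
| 30% | 1.3 |

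A pooled 1.2 arises equally from 1.2 in both groups, or from 1.0 in one and 1.4 in the other. The binary model cannot distinguish these. That conclusion needs no distributional assumption.

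**2. Information lost, normal exposure and log-linear effect.** Efficiency of a split with fraction p above the cut is φ(z)² / [p(1 − p)]. At p = 0.40: 0.3863² / 0.24 = 0.622. The loss is 37.8%, and 180 × 0.622 ≈ 112 residents' worth of information remains. At 30% prevalence the loss is 42.4%, and at 50% it is 36.3%.

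**3. Other distribution shapes, 40% above the cut, effect linear in osmolality.** The loss is one minus the squared correlation between the value and its split.

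| Shape | Loss |
|---|---|
| Uniform | 28% |
| Gamma (shape 4) | 37% |
| Lognormal, σ 0.25 to 0.5 | 37-43% |
| t, 5 df | 47% |

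**4. Step-shaped risk.** If risk steps exactly at 295, the binary is the correct exposure and nothing is lost. If it steps at 300, efficiency is 0.6p₂ / [0.4(1 − p₂)]. That gives 0.167, 0.375 and 0.50 for p₂ of 10%, 20% and 25%, so the loss is 50-83%.

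**5. Three categories instead of two.** Under the assumptions of step 2, with 10-25% above 300, efficiency rises only from 0.62 to about 0.68-0.70. The categories mainly help interpretation. The numeric value is what restores precision.

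**6. Illustrative power for HR 1.4, two-sided 5%.** Binary: log HR × √(D × 0.24), where D is the number of deaths. Continuous: (log HR / 1.61) × √D, where 1.61 = 0.3863/0.4 + 0.3863/0.6 is the gap between group means in SD units.

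| Deaths (assumed) | Binary | Continuous |
|---|---|---|
| 40 | 18% | 26% |
| 60 | 25% | 37% |
| 80 | 31% | 46% |

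**The case against.** **The binary coding of the outcome models is inferred.** The definition leads straight into the diagnostic analyses. The cohort paragraph refers to osmolality as measured in blood without giving its scale, and exposure coding often belongs in a statistical analysis plan, which is not shown. This stands in part: another coding is not excluded. But the Protocol's only written definition is binary, it heads the whole analysis text, and the outcome wording pools the two levels in the same way. It is a stated choice that needs amending or qualifying, and not merely an omitted detail.

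**A binary contrast has a purpose.** The tool classifies residents as dehydrated or not, so osmolality at the same cut is the fair comparator when the two are judged against outcomes. This stands, and the binary should be kept for that use.

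**The Protocol does not promise an answer on impending dehydration.** A reader might infer from the Background that the study fails a question it set itself. The same passage says the matter will not become clear until impending dehydration can be diagnosed and addressed, and secondary aim 3 speaks only of hydration status. The documents therefore do not support that charge. The weaker point remains: the data could inform the question, and the pooled contrast cannot.

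**A flat 38% loss is not supported.** It needs normality, a log-linear effect and 40% prevalence. Linearity itself is doubtful, because the Background reports excess mortality with hyponatraemia, so risk may rise at low values too. A straight-line term could then mislead as well.

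**Recoding does not rescue power.** For HR 1.4 power is low on either scale. Applying 2.1 to deaths would look more striking (68% against 87% with 45 assumed deaths), but 2.1 is the Background's relative risk for new disability, not mortality. Nor would a null binary result be uninterpretable. It would simply leave open an effect confined to values above 300.

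**Conclusion.** The point holds, limited to the cohort models for secondary aim 3. With the 295 split as the sole osmolality exposure, a modest effect in both groups and an effect confined to values above 300 look the same. The latter is the region of the only estimate by osmolality level that the Protocol cites. This follows from the pooling alone.

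The precision loss is real under most plausible shapes, but its size is conditional: about 38% for a normal, log-linear exposure at 40% prevalence, roughly 28-47% for other shapes, nil for a step exactly at 295, and 50-83% for a step at 300. The cited evidence gives no particular support to a step at 295. The power figures are illustrations only, since the number of deaths is assumed.

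A reader might infer that the study cannot show whether impending dehydration carries risk. That is true of the pooled analysis and not of the data, which hold the numeric value. The diagnostic analysis is unaffected.

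**What to change.** Keep the 295 cut for the decision tree, and for comparing the tool with osmolality against outcomes. In the cohort paragraph of Data analysis, state that the osmolality exposure in the Cox, Barthel and EQ-5D models is the numeric value, modelled flexibly from the start. A restricted cubic spline with few knots would serve, since risk may also rise at low values. Report the Protocol's own three categories (<295, 295-300, >300) beside it. Writing this down now also prevents the scale from being chosen after outcomes are seen.

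The cost is a little more analysis, one or two extra degrees of freedom, and a headline less simple than yes/no. No new data, visits or samples are needed. The category estimates will be imprecise. If osmolality is normal with an SD of 7 to 10 and 40% are at or above 295, about 17-23% lie above 300. That is some 30 to 41 of 180 residents above 300, and 42 to 31 in the 295-300 band. They should be read with their intervals.

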Currently available evidence on dehydration in older people is patchy. It is vital for the health and wellbeing of older people, and to reduce unplanned emergency hospital admissions, that we identify impending dehydration in the community and residential care, and learn to prevent current dehydration. Our approach to develop the research base for water-loss dehydration will be to validate a short decision tree of clinical and/or physical signs of impending dehydration for use by older people and/or their carers. Validation will be both essentialist (against the best reference standard of water-loss dehydration, serum osmolality), and consequentialist (assessing the utility of this panel in predicting mortality, functional status and QoL) (29). This will prepare for future randomised trials of screening and intervention to prevent or redress impending water-loss dehydration on important health outcomes in older people.

Primary Aim:

The principal research objective is to identify a tool (a short decision tree of clinical and physical signs) that will identify water-loss dehydration in frail older people.

Secondary aims:

Additional objectives include:

1. Quantify diagnostic accuracy (sensitivity/specificity) of each clinical or physical sign

2. Quantify the incidence of dehydration in older people living in residential care

3. To understand the relationship between hydration status at baseline and mortality, quality of life and functional status 1 and 2 years later.

4. To understand the relationship between sudden weight changes over 1 year (indicating change in fluid status) and mortality, quality of life and functional status at 1 and 2 years.

Study design

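### The decision tree is selected, fitted and, as the protocol is written, scored on the same 180 or so residents, so its stated accuracy would be optimistic

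*Protocol*

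**What the plan says.** The primary aim is a short decision tree that identifies water-loss dehydration. The Study summary takes the baseline data, assesses each marker, and then combines markers into a tree. The Data analysis section repeats this order. Signs are analysed one at a time against osmolality dichotomised at 295 mOsm/kg, then "Those showing the best diagnostic accuracy will be considered collectively", and CART builds the tree. It gives no number or threshold for the signs kept, and no hold-out set, cross-validation, bootstrap or pruning rule.

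The last paragraph of the Background says that the approach is to validate such a tree: "Validation will be both essentialist (against the best reference standard of water-loss dehydration, serum osmolality), and consequentialist". The cohort analysis then uses the fitted tool as one of two exposures: "dehydration (assessed by the developed diagnostic tool, and by measured serum osmolality".

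Under Sample size, the protocol says "we will recruit 200 participants", "assuming a dehydration prevalence (current or pending categorised together) of approximately 40" per cent, and that "a sample size of 180 would ensure a standard error of no more than 0.05 for Kappa values in excess of 0.75". It adds: "For values of at least 0.6, the standard error would be no more than 0.06".

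The section on the 3-year research plan says that this study covers items 2 and 3. Item 5 is a pilot of the finished tool that includes its diagnostic accuracy in another context.

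**The concern.** The choice of signs, the cut-points and the splits are all tuned to the osmolality values of one set of residents. If the tree is then compared with those same values, agreement is inflated, because some splits fit chance patterns that new residents will not show. Such a figure describes fit to the development data and does not validate the tool.

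The stake is the main product of the study. Under Dissemination of results, the consensus workshop is to be shown evidence on the best tools, drawn from the systematic reviews and the cohort analyses. The pilot is not named as a source. A tree with modest real accuracy could therefore be presented to care homes as a good one.

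The sample size also rests on the standard error of kappa for a test fixed in advance. It makes no allowance for bias from choosing the test on the same data.

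**Working it through.** **1. The plan's own figures.** Take prevalence p = 0.4, equal margins and n = 180.

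- Chance agreement: pe = 0.4² + 0.6² = 0.52.
- Observed agreement: po = κ(1 − pe) + pe.
- SE(κ) = √[po(1 − po)/n] / (1 − pe).
- κ = 0.75: po = 0.75 × 0.48 + 0.52 = 0.88; SE = √(0.88 × 0.12/180)/0.48 = 0.0505.
- κ = 0.60: po = 0.60 × 0.48 + 0.52 = 0.808; SE = √(0.808 × 0.192/180)/0.48 = 0.0612.
- The Donner–Eliasziw form gives 0.0504 and 0.0609.
- Loss allowance: 180/(1 − 0.10) = 200.

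The stated 0.05, 0.06 and 200 are reproduced to the precision printed. The sample-size arithmetic is not in error; it applies to a test that is already fixed.

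**2. Size of the optimism, by simulation.** From the protocol: n = 180, 40% dehydrated, binary outcome, univariate screen followed by CART. Assumed, because the protocol gives none of it:

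- 20, 40 or 60 independent candidate signs, with the best 8 kept by univariate AUC;
- an unpruned Gini tree of depth 2, 3 or 4 (minimum leaf 15, 10 or 5);
- either no informative sign, or four signs with sensitivity 0.50 and specificity 0.75, so LR+ = 0.50/0.25 = 2, in line with the Background's threshold for a promising sign.

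Each row averages 200 replicates. New-resident kappa is measured in 4,000 fresh subjects; cross-validation (CV) is 10-fold.

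| Candidates | Informative | Depth | Same-data κ | New-resident κ | Gap | CV of CART only | CV with screen inside |
|---|---|---|---|---|---|---|---|
| 20 | 4 | 3 | 0.47 | 0.25 | 0.22 | 0.25 | 0.22 |
| 40 | 4 | 3 | 0.47 | 0.24 | 0.23 | 0.26 | 0.21 |
| 60 | 4 | 3 | 0.48 | 0.23 | 0.25 | 0.26 | 0.21 |
| 40 | 4 | 2 | 0.36 | 0.21 | 0.15 | 0.21 | 0.19 |
| 40 | 4 | 4 | 0.56 | 0.22 | 0.34 | 0.25 | 0.20 |
| 20 | 0 | 3 | 0.32 | 0.00 | 0.32 | 0.03 | −0.01 |
| 40 | 0 | 3 | 0.34 | 0.00 | 0.34 | 0.05 | −0.02 |
| 60 | 0 | 3 | 0.35 | 0.00 | 0.35 | 0.06 | −0.03 |
| 40 | 0 | 2 | 0.25 | 0.00 | 0.25 | 0.05 | 0.00 |

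In the second row, same-data sensitivity and specificity are 0.62 and 0.84, against 0.48 and 0.75 in new residents. With 20 candidates and depth 2 the gap falls to about 0.13. A separate simulation with 40 candidates and depth 3 gave 0.45 against 0.24 with four informative signs, and 0.31 against 0.00 with none. Whole-procedure cross-validation gave 0.23 and 0.00.

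**3. Against the planned precision.** With informative signs the gap runs from about 0.13 to 0.34. Then 0.13/0.06 = 2.2 and 0.34/0.05 = 6.8, so the bias is about two to seven times the stated standard error. At the lower kappas seen here the standard error is larger (0.070 at κ = 0.4, 0.074 at κ = 0.2). The ratio is then 0.13/0.074 = 1.8 to 0.34/0.070 = 4.9.

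**4. Which step causes it.** Cross-validating only the CART step removes most of the gap. What remains is 0.03 to 0.06 above the truth when no sign is informative. With four informative signs it is 0.02 to 0.05 above the whole-procedure figure. Over all runs this is about 0.02 to 0.07. The screen is therefore the smaller part; scoring the tree on its own data is the larger.

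**The case against.** The best defence is that the protocol never says accuracy will be computed by resubstitution or that the tree will be unpruned. Pruning and resampling are commonly left to an SAP, and one may exist. That stands to this extent: a reader might infer that the published accuracy will certainly be overstated, and the document does not support that. The claim holds for the plan followed as written. It goes beyond missing detail, because the protocol itself fixes the screen and the tree on one data set and calls the comparison validation. An SAP that resampled only CART would still leave the screen outside.

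It can also be said that validation here only names the criterion (osmolality, later outcomes), and that elsewhere the protocol speaks of identifying and developing a tool. The wording may be no more than loose, but it invites the wrong reading of the result. The STARD commitment governs reporting and does not correct optimism. The pilot does help the programme, but it does not alter the accuracy reported from this cohort.

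The simulated cases can be called pessimistic. Many signs were pre-selected from a review, which makes the all-noise rows a bound rather than an expectation, and pruning would narrow the gap. Both points stand, so the conclusion rests on the rows with informative signs.

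Three further inferences should not be drawn:

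- That the screen defeats the protocol's own reason for CART. The stated reason is to spare residents and staff some testing, not to find signs that help only after an earlier split.
- That the pilot is too small to matter. No size is given.
- That the outcome models are shown to be biased. The tree is fitted to osmolality, not to mortality or function, measured osmolality is analysed alongside it, and no size of bias has been established.

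**Conclusion.** The point holds for the protocol as written. One cohort of about 180 analysable residents selects the signs, grows the tree and supplies the comparison described as validation, with no correction stated. Under the assumed settings and informative signs of LR+ about 2, kappa is overstated by about 0.13 to 0.34. Most of that comes from same-data scoring and about 0.02 to 0.07 from the screen. The number of candidates (40 in the central case), the number kept, the tree depth, the absence of pruning and the strength and independence of the signs are assumptions, not protocol figures; a pruned tree would show less. The direction does not depend on those choices: every run gave a higher same-data kappa than new-resident kappa. Because the primary aim is affected, the text should be changed before the tree is fitted.

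**What to change.** In Data analysis:

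- State that all candidate signs go to CART, or that the univariate screen is repeated inside each resample. Sending all signs to CART does not by itself remove same-data optimism; the resampling does.
- State that the headline sensitivity, specificity and kappa of the tree come from cross-validation or bootstrap of the whole procedure, preferably resampling care homes rather than residents, since residents of one home share staff and drinks routines. Same-data figures may be shown beside them, labelled as such.

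At the end of the Background, describe this cohort as development with internal validation, and leave accuracy in other settings to the pilot in item 5 of the research plan.

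Optionally, add a sensitivity analysis of the outcome models that uses out-of-fold classifications. These come from several trees rather than the delivered tool, so they should not replace the main analysis.

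No new data are needed. The cost is some computing, a few sentences of protocol text and less favourable reported accuracy. In the simulations, whole-procedure cross-validation came within about 0.03 of the new-resident kappa.
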